The frequency and nature of deviations from the pain scale script at the initial pain assessment in triage will be directly observed by the PI and audio recorded for future word-for- word analysis of deviations from the script. The audio recordings will be used to make transcripts devoid of PHI for this purpose. Field notes will be taken by the PI in order to provide context and other key observations not captured by the audio recordings. Variations from the transcript will be identified and quantified. Field notes, coupled with quantitative data of the frequency of deviations from the pain scale script and their location within the script will be analyzed by qualitative methods of interview analysis described in the Qualitative Analysis Guide of Leuven, modified to analyze our observations.⁷ Briefly, the data of the script deviations and field notes will be conceptualized, whereby the data will be filtered and the most important data clustered into concepts to prepare for analysis. The transcripts and field notes will be re-read with the concepts in mind and refined. The individual transcripts will be assessed by the constant comparative method with review of common themes and the identification of new themes. Concepts will be integrated into a conceptual framework relating to the hypothesis and discussed with the research team to obtain consensus prior to generating a final summary of concepts.

Phase 2 – Primary Aim #1:

To determine if level of neurocognitive development impacts responsivity of the WBF and FPS-R (whether the measure is able to identify changes in pain over time that are clinically important to patients) when used in the pediatric ED with children presenting with acute pain.

Hypothesis: Patients with at or above expected cognitive development will exhibit improved responsivity when using the WBF and FPS-R compared to children with lower than expected cognitive development. Those who can successfully complete behavioral tasks such as matching and grouping will exhibit improved responsivity when using the WBF and FPS-R compared to children who cannot complete such tasks successfully.

Phase 2 – Primary Aim #2:

To determine the cognitive age equivalent at which children presenting to the emergency department with acute pain can use the WBF and FPS-R accurately to self-report their level of pain at two separate time points during their ED evaluation.

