Hypothesis: Children with a cognitive age equivalent of at least five years old will more reliably use the WBF and FPS-R to self-report acute pain when presenting to the emergency department

Rationale: Multiple studies have compared children's ability to use pain scales based on age, and both the WBF and FPS-R are conventionally believed to be appropriate for children once they are four years old. However, age is used as a proxy for developmental level; not all four year old children have the developmental and cognitive skills to quantify and report their pain. Whether children have the skill set to complete a self-report of pain is variable until approximately the age of five years. This study would serve to more clearly classify the level of cognitive development needed to use the pain scales effectively.

Methods Summary: Prospective, observational study to determine if there is correlation between neurocognitive development and responsivity when using the WBF and FPS-R as well as the minimum cognitive age equivalent needed to effectively use the WBF and FPS-R. Initial and repeat WBF and FPS-R self-report scores will be compared at two points during the ED evaluation of patients presenting with acute pain. The change in the WBF and FPS-R pain scores will be compared to the subjective self-reports of change in pain. Children will complete the BRIGANCE ® Early Childhood Screens III to determine whether they are at, above, or below the expected cognitive development for their age. Children with at or above expected cognitive development. Children will also complete a series of tasks aimed to assess ability to successfully use the WBF and FPS-R (Appendix 2). Children that complete all tasks successfully will be compared to those who do not. The BRIGANCE will also be used to determine the cognitive age equivalent for each subject. We will determine the minimum cognitive age equivalent for each subject. We will determine the minimum cognitive age equivalent for each subject. We will determine the minimum cognitive age equivalent associated with accurate use of the WBF and FPS-R, defined as a self-report that matches the subjective report of change in pain.

Phase 2 – Secondary Aim #1:

To determine whether the WBF and FPS-R exhibit convergent validity (degree to which they produce similar results) when used with children presenting to the emergency department with acute pain

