Exclusion criteria

Altered mental status History of traumatic brain injury (TBI) History of developmental delay History of Autism History of chronic pain, defined as persistent or recurrent pain in children with chronic health conditions⁸ Non-verbal patients

Outcome Measures:

Phase 1 - Primary Aim

Rate of intended script use in pain scale delivery Review of themes during nursing pain assessment Consistency in delivery of WBF by nursing

Phase 2 - Primary

Neurocognitive development score BRIGANCE ® score Initial WBF score Repeat WBF score Initial FPS-R score Repeat FPS-R score Anchor report of pain (a lot better, a little better, the same, a little worse, a lot worse)

Phase 2 - Secondary

Initial WBF score (patient and caregiver) Repeat WBF score (patient and caregiver) Initial FPS-R score (patient and caregiver) Repeat FPS-R score (patient and caregiver)

Study Definitions:

"Caregiver" will refer to an adult who is able to provide consent for treatment and provides regular care for the child.

"Chronic pain" includes persistent (ongoing) and recurrent (episodic) pain in children with chronic health conditions.

Convergent validity evaluates the degree to which two different scales that are supposed to measure the same thing produce similar results.

"Repeat pain score" will be completed approximately 20 minutes after the initial pain score, or if administered, approximately 20 minutes after analgesic intervention.

Responsivity is the degree to which a test behaves in a manner that is consistent with what the test is purported to measure. It determines whether the measure is able to identify changes in pain over time that are clinically important to patients.

Phase 1 Study Protocol:

- 1. Once the subject is identified, the caregiver will provide verbal consent for participation in the study.
- 2. After verbal consent is obtained, the primary investigator will observe and audio record nursing's assessment of the patient's pain and complete the observation checklist (Appendix 1).

Phase 2 Study Protocol:

- 1. Once the subject is identified, the caregiver will provide written consent for participation in the study (if a self-report pain score was not collected in the triage process, patients with pain or a potentially painful condition will have their pain assessed using an age appropriate self-report pain scale by the PI or designee).

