Responsivity will be measured by correlating the change in the WBF and FPS-R scores before and after analgesic intervention with the anchor change in pain score (a lot better, a little better, the same, a little worse, a lot worse). Pearson correlations will be estimated between each change score and the anchor score. In addition, we will use ANOVA to test the difference in mean pain change among the children reporting "a lot better", "a little better", and "the same". For the scales to be considered responsive, we would need to see significant reductions for the children reporting "a lot better", minimal to no reduction for those reporting "the same", and increase in pain for those reporting "worse". We will need a relatively large number of children in each category (a lot better, a little better, the same) to be able to test for differences (at least 30 per group). We will use Fisher's z-transformation to test if level of neurocognitive development impacts responsivity. Levels of neurocognitive development will be defined as at or above expected or lower than expected. The Fisher's z-transformation formally tests if the correlations between two measures (change in pain and anchor rating) differ between two groups. Here we assume we will have significant variability in change scores and in the anchor ratings to conduct these correlations and the formal test. We would need at least 56 children in each neurogcognitive development group (expected or above versus below). If the variability is limited in that most children report improvement and few report same or worsening, we will test for responsivity differences using a two-way ANOVA where the two factors are self reported anchor response ("better", "same" or "worse) and neurocognitive level (expected or above expected vs below expected). The outcomes are the change in the WBF and the change in the FPS-R. The test of interest will be the two way interaction between the anchor and the neurocognitive development level. The BRIGANCE also provides the developmental age for each child which can be compared to their actual age. We will test if this difference is significant using a paired t-test. We will also explore the age where responsivity worsens by conducting similar analyses but stratified by actual age (each year) and developmental age. Given the proposed analysis, we will need at least 50 children for each cognitive age (3, 4, 5, 6, and 7 years) assuming at least 10 fall into the "a lot better", "a little better", "the same" categories for the anchor pain question.

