Appendix 3 – Patient Survey (Phase 2 Primary and Secondary Aims)

Part One

Time: _____

1. Does anything hurt on you right now?

2. Faces Pain Scale-Revised reported score:

3. Wong-Baker FACES ® reported score:

Medication:

Time administered: _____

Part Two

Time:									
1. Do you feel	better, wors	e, or the same	?						
Better (go to Se	ection A)	Worse (go to Section B)		Same (go to Section C)					
Section	пA								
	Do you feel	a little bit bette	r or a lot bett	er?					
	A little	e bit	A lot						
	Does anything hurt on you right now?								
	Yes	0 ,	No						
,	What hurts on you right now?								
Section	n B								
Do you feel a little bit worse or a lot worse?									
	A little	e bit	A lot						
	What hurts on you right now?								
	🗆 MD notifie	ed							
Sectior	n C								
I	Does anything hurt on you right now?								
	Yes		No						
	What hurts on you right now?								
	🗆 MD notifie	ed							
2 Eason Dain	Saala Bavia	ad reported as							

2. Faces Pain Scale-Revised reported score:

3. Wong-Baker FACES ® reported score:

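### Primary Aim #2 has no pre-specified analysis: its match definition goes unused, cognitive age under 5 is never contrasted with 5 and over, no rule names the minimum age, and about 250 children leave no margin for 50 per cognitive age

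*Combined protocol and SAP*

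**What the plan says.** Phase 2 Primary Aim #2 is "To determine the cognitive age equivalent at which children presenting to the emergency department with acute pain can use the WBF and FPS-R accurately". Its hypothesis sets a cut: "Children with a cognitive age equivalent of at least five years old will more reliably use the WBF and FPS-R". Its Methods Summary promises to find the lowest such age "associated with accurate use of the WBF and FPS-R, defined as a self-report that matches the subjective report of change in pain".

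The Phase 2 part of Statistical Analysis correlates score change with the child's anchor answer, compares mean change across anchor groups by ANOVA, and gives a criterion for group means that begins: "For the scales to be considered responsive, we would need to see significant reductions for the children reporting". The remainder of that criterion expects little or no fall in children who feel the same and a rise in those who feel worse. The formal subgroup test is Fisher's z, with these groups: "Levels of neurocognitive development will be defined as at or above expected or lower than expected". On age, the section says: "We will also explore the age where responsivity worsens by conducting similar analyses but stratified by actual age (each year) and developmental age".

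The same section requires at least 50 children at each cognitive age from 3 to 7, assuming at least 10 in each of three anchor categories. The stated Phase 2 size is approximately 250. The data needed for a match are collected: Outcome Measures lists both scores at both times and "Anchor report of pain (a lot better, a little better, the same, a little worse, a lot worse", and Part Two of the Patient Survey (Appendix 3) asks for direction and degree, for example "Do you feel a little bit worse or a lot worse".

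**The concern.** A primary aim with a stated hypothesis is served only by an exploratory sentence. Followed as written, the plan yields a set of yearly correlations and ANOVAs for each scale, and someone must then decide which of them marks the minimum age. That decision would be made after seeing the data, and reasonable choices can name different ages. The five-year hypothesis itself would have no test.

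The sample-size sentence adds a second difficulty. It sets a floor for every cognitive age, but the total equals the sum of the floors, and cognitive age is not known at enrolment because BRIGANCE comes last.

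**Working it through.** **1. Aim against analysis.**

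| Aim #2 needs | Phase 2 analysis provides |
|---|---|
| Match between self-report and reported change | Correlations and group mean changes; no match is defined |
| Comparison at a cognitive age of five | Fisher z on at-or-above versus below expected development |
| A minimum age | Exploratory yearly strata; no naming rule |

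The Fisher z groups are relative to age: a 3-year-old and a 7-year-old who are both at the expected level fall in the same group. The test therefore serves Aim #1 and cannot stand in for a contrast at five. If the correlation and the ANOVA are both repeated, five developmental-age strata x 2 scales x 2 analyses give 20 results, before the parallel set by actual age.

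**2. Does the unstated rule matter?** An illustration at the plan's own 50 per stratum: bivariate normal data, 20,000 simulated studies, assumed true correlations at cognitive ages 3 to 7. Rule A is the youngest year with a significant correlation; rule B is the youngest year with r of at least 0.5. Neither rule is in the plan.

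- 0.3, 0.3, 0.6, 0.6, 0.6: same age in 23%.
- 0.3, 0.4, 0.5, 0.6, 0.7: same age in 18%.
- 0.1, 0.1, 0.6, 0.6, 0.6: same age in 69%.

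Precision of one stratum, by tanh(atanh r +/- 1.96/sqrt(n-3)): r = 0.5 has a 95% CI of 0.26 to 0.68 with 50 children.

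**3. The plan's total.** 5 cognitive ages x 50 = 250, which reproduces the stated size with a margin of zero.

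- Equal shares, no loss: the smallest of five strata averages 41.9 of 250. The chance that all five reach 50 is 250!/(50!^5 x 5^250) = 0.00002, since each must be exactly 50.
- 10% loss (assumed): 225 children, 45 per age on average; the smallest averages 37.3.
- Uneven ages (assumed): actual age uniform over 3 to 7.5 years, cognitive age offset by -0.5 to +0.5 year with SD 0 to 1 year. The 7-year stratum then expects between 0 and 56 of 250, and the 3-year stratum between 28 and 56. The share under 5 is 0.33 to 0.56.

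**4. Why raw match cannot be the test.** If anchor answer and score direction are unrelated, chance match is the sum of the products of their shares (better, same, worse; all assumed):

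- both 50/30/20: 0.25 + 0.09 + 0.04 = 0.38
- 70/20/10 with 60/25/15: 0.42 + 0.05 + 0.015 = 0.485
- 85/10/5 with 75/15/10: 0.6375 + 0.015 + 0.005 = 0.66

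Two age groups that improve at different rates could thus differ in raw match with no difference in understanding.

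**5. What a pooled contrast gives.** Assume 225 completers (90%) and 44% under 5: 100 versus 125. The standard error of the difference in Fisher z is sqrt(1/97 + 1/122) = 0.136, so the 95% CI half-width is 1.96 x 0.136 = 0.27. With 80% power and two-sided 0.05, the detectable difference is 2.80 x 0.136 = 0.38 on that scale, for example r = 0.30 against 0.60.

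**The case against.** The plan is not silent. It has a directional criterion for responsiveness, its yearly strata would give an estimate at age five, and the aim's data are all collected. That stands, and it rules out the reading that the trial cannot address the aim. But the criterion concerns group means, has no figures, and is not tied to naming an age. The list of outcome measures is also weak evidence against a match outcome: it omits change scores too, yet the analysis uses them.

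The simulated rules are not the plan's, and the result depends on the assumed correlations. That stands; the percentages show only that the choice of rule can matter.

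Some stronger inferences do not hold:

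- A reader might infer that the plan expects few children to feel the same or worse. It treats this as a contingency with a fallback analysis; its working assumption is adequate variability.
- A reader might see a contradiction between 30 per anchor group and 10 per category. The first is for the pooled ANOVA, the second an explicit assumption for the exploratory strata.
- A reader might conclude that the 7-year stratum must fall short. An expected count of 28 follows from one scenario (cognitive age equal to actual age, uniform ages); the assumed range reaches 56.
- The total is approximate, so it is not a cap. Even so, no allowance or quota by cognitive age is stated.

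**Conclusion.** The gap is real and should be corrected before analysis. Primary Aim #2 has a verbal definition of accuracy that the analysis does not use, a five-year hypothesis with no test, and a target age with no naming rule. This follows from the text alone and depends on no assumed rate.

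The sample-size point is secondary. The zero margin is arithmetic. The average of 42 in the smallest stratum assumes equal shares and full completion; other stratum figures depend on an age distribution that the documents do not give. Together with convenience sampling, entry ending at 7 years 6 months, and a final BRIGANCE that the child may decline, they show that about 250 does not secure 50 at each cognitive age. They do not forecast any particular count.

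**What to change.** 1. **Test of the five-year hypothesis.** For each scale, use the plan's own Fisher z comparison of the change-anchor correlation between cognitive age under 5 and 5 and over, in all BRIGANCE completers, with a 95% CI. If variability is limited, use the plan's two-way ANOVA fallback with the same two age groups.
2. **Per-child match.** For each scale, score down, unchanged or up against better, same or worse, with a stated rule for a child already at the lowest or highest face. Report it by age group with a chance-corrected measure such as weighted kappa on the five-level anchor, with score-change cut-offs fixed beforehand so that the degree of change is kept. Do not rely on raw match alone.
3. **Minimum age.** Model responsivity or match on continuous BRIGANCE developmental age. Before analysis, fix the level (above chance) and the rule that name the age. Report the age with its CI, or as not reached or not estimable.
4. **Yearly results.** Keep them descriptive.
5. **Sample-size sentence.** Replace the floor per age with a range of expected, unequal stratum counts, an assumed BRIGANCE completion rate and the resulting precision. No extra enrolment is needed.

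The cost is wording in the statistical section. The losses are that yearly results are no longer inferential, the model assumes a smooth relation with age, and the level must be agreed in advance. The threshold age may also be very imprecise. In 2,000 simulated studies of 225 completers with match rising only from 60% at age 3 to 80% at age 7 (assumed), the CI was finite in about 61% to 64%; its median half-width was about 1.6 years at a 70% level and about 2.8 years at an 80% level. The pre-specified contrast in item 1 does not depend on locating that age.

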Hypothesis: The WBF and FPS-R will demonstrate convergent validity when used to measure acute pain in children presenting to the emergency department

Rationale: Both the WBF and FPS-R have been studied for their use in obtaining self-reports of pain in children, and overall have been determined to be two of the preferred methods of pain assessment in pediatric patients. Although each has been compared to other methods of pain measurement, the two have not been compared to each other. If the two studies were proven to have convergent validity, it would strengthen the evidence that these methods should be the preferred tools for assessing pain in children.

Methods Summary: Prospective, observational study to determine the convergent validity of the WBF and FPS-R for children presenting to the ED with acute pain. The initial and repeat WBF and FPS-R self-report scores will be compared in patients presenting to the ED with acute pain.

Phase 2 – Secondary Aim #2

To determine if there is inter-rater reliability between patients presenting to the pediatric ED with acute pain and their caregivers when using the WBF and FPS-R at two separate time points during their ED evaluation

Hypothesis: There will be low inter-rater reliability between patients and their caregivers using the WBF and FPS-R.

Rationale: Caregiver perception of a pediatric patient's pain is often used as a substitute for the patient's self report of pain; however, studies are limited to show that caregivers are able to predict children's pain level accurately when in the acute care setting.

Methods Summary: Prospective, observational study to determine the inter-rater reliability between patients and their caregivers when using the WBF and FPS-R. The initial and repeat WBF and FPS-R self-report scores will be compared to caregivers' initial and repeat WBF and FPS-R ratings in patients presenting to the pediatric ED with acute pain.

Identification of Subjects

Participants will come from a convenience sample of children presenting to the ED. Triage nurses and ED providers will be aware of the study and notify the PI or designee by phone if patients may qualify for the study. The PI and designees will also have access to the ED trackboard and can screen for possible participants.

Inclusion Criteria

Patients \geq 3 years and \leq 7 years six months old Chief complaint of pain or painful condition (Phase 1 only) Pain score \geq 4/10 (Phase 2 only) Caregiver speaks English or Spanish

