- 2. Early in the ED visit, the investigator or designee will help the patient complete Part One of the Patient Survey (Appendix 3), which includes the WBF, and the FPS-R.
- 3. The caregiver will also complete Part One of the Caregiver Survey (Appendix 4).
- 4. Subjects will be treated per usual care by an MD/ACP.
- 5. The investigator or designee will help the patient complete Part Two of the Patient Survey (Appendix 3), which includes the WBF and the FPS-R. This will occur approximately 20 minutes after analgesic administration, if it was ordered.
- 6. The caregiver will also complete Parts Two and Three of the Caregiver Survey (Appendix 4).
- 8. If the patient indicates that he/she feels the same or worse on Part Two of the Patient Survey the treating MD/ACP will be notified.
- 9. The patient will be reassessed by the PI or designee at least 20 minutes after analgesic administration, if it was ordered, or after a reasonable time period if no analgesic medication was ordered.
- 10. On reassessment, if the patient says that he/she is willing to participate, the PI or designee will complete a brief neurocognitive skills assessment (Appendix 2) as well as the BRIGANCE ® Early Childhood Screens III with the patient. If the patient is not willing to participate, study assessments will cease.

Statistical Analysis:

Phase 1

Sample size: 30

Rate of compliance with intended script and rate of consideration of caregiver perception will be reported as percentages. Qualitative data will also be reviewed by the PI for the emergence of themes.

Phase 2

Sample size: approximately 250

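### The minimum of 50 children at each of five cognitive ages takes up the whole planned Phase 2 sample of about 250, and the design cannot be expected to deliver it in every stratum

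*Combined protocol and SAP*

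**What the plan says.** The combined protocol and SAP gives the Phase 2 size under Statistical Analysis as "Sample size: approximately 250". The same section plans to explore where responsivity worsens by repeating the analyses within each year of actual age and of developmental age. For that it says "we will need at least 50 children for each cognitive age (3, 4, 5, 6, and 7 years", with a condition attached: "assuming at least 10 fall into the" three anchor categories of much better, slightly better and unchanged.

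Four other places bear on whether this number can be reached:
- Identification of Subjects: "Participants will come from a convenience sample of children presenting to the ED". No quota by age is stated.
- Inclusion Criteria: entry runs from age 3 to "7 years six months old".
- Phase 2 Study Protocol, step 10: the BRIGANCE, which supplies cognitive age, is given at reassessment to willing children. "If the patient is not willing to participate, study assessments will cease".
- Statistical Analysis, on developmental versus actual age: "We will test if this difference is significant using a paired t-test". The exclusion criteria also list "History of developmental delay". The relation between the two ages in this sample is therefore left open.

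**The concern.** The minimum is stated as a need in every stratum, yet the strata together use the entire sample. Any unevenness across ages, and any child without a BRIGANCE, takes at least one stratum below 50 unless more than 250 are enrolled. The documents describe no mechanism that evens out the strata, and cognitive age is known only after testing.

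The by-year work is the only statistical method the section gives for locating an age threshold, which is the subject of Phase 2 Primary Aim #2. Readers would take the stated 50 as the footing of each yearly result, when some years are likely to rest on fewer children and may not meet the plan's own condition on anchor categories.

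**Working it through.** **Inputs from the documents.** Total about 250; five cognitive ages; at least 50 in each; at least 10 in three anchor categories; entry from 3.0 to 7.5 years. No alpha, power or effect size is given for the 50, so no power formula applies. Age mix, BRIGANCE refusal and anchor shares are not given; values used for them below are assumptions.

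**1. The plan's figure.** 5 × 50 = 250. The planned total is reproduced exactly, with nothing left over.

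**2. Equal shares, no loss.** Stratum counts are multinomial(N; 0.2, 0.2, 0.2, 0.2, 0.2). This is the most favourable age mix under random enrolment. By simulation:

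| Children with a BRIGANCE | Median smallest stratum (5th–95th percentile) | All five reach 40 | All five reach 45 | All five reach 50 |
|---|---|---|---|---|
| 250 | 42 (36–47) | 78% | 24% | under 0.01% |
| 260 | 44 (37–49) | 88% | 46% | 1.7% |
| 275 | 47 (40–52) | 96% | 74% | 21% |

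**3. Missing BRIGANCE, if 250 means enrolled.** Mean per year = 250 × (1 − d)/5. With d = 10% this is 45, and with d = 20% it is 40 (both rates assumed). The median smallest stratum is then 38 or 33.

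**4. Actual-age strata.** The year-7 band covers half a year of a 4.5-year entry range. With uniform ages (assumed), 250 × 0.5/4.5 = 28 children at age 7 and 250 × 1/4.5 = 56 at each other age.

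**5. Cognitive-age strata.** Take uniform actual age plus a normal difference (cognitive minus actual) with SD 0 to 1.0 year, all assumed. Expected counts out of 250, with children under 3 or aged 8 and over placed in the end strata:

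| Mean difference (years) | Below 4 | 7 or above |
|---|---|---|
| −0.5 | 83–85 | 0–22 |
| −0.25 | 69–72 | 14–30 |
| 0 | 56–60 | 28–39 |
| +0.25 | 42–49 | 42–49 |
| +0.5 | 28–39 | 56–60 |

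In every row at least one end is expected below 50, but which end depends on the mean difference. Years 4 and 5 hold 46 to 56 throughout.

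**6. The plan's own condition.** Read as 10 in each of the three anchor categories, it needs at least 30 children. Chance that it holds, for assumed shares (much better / slightly better / unchanged / worse):

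| n in the year | 30/30/30/10% | 40/30/20/10% |
|---|---|---|
| 50 | 88% | 52% |
| 42 | 57% | 24% |
| 38 | 32% | 11% |
| 33 | 4% | 1% |
| 30 | 0.1% | under 0.1% |

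These depend strongly on the shares. At n = 50 the chance is about 10% with 20% in each of the five answers and 96% with one third in each of the three categories.

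**7. Precision.** For an illustrative r = 0.50, the Fisher-z 95% interval is tanh(atanh 0.50 ± 1.96/√(n − 3)): 0.26–0.68 at n = 50, 0.23–0.70 at n = 42 and 0.16–0.74 at n = 28.

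**The case against.** The total is only approximate, the 50 has no stated power basis, and the by-year work is introduced as exploratory. Staff can screen the ED trackboard, so nothing rules out steering enrolment by actual age; independent draws are a model, not a fact in the documents. A fall from 50 to 42 barely widens an interval, and years 4 and 5, around the hypothesised threshold of five, stay near 50 before refusals. All of this stands, and it limits the weight of the point. It does not supply the missing slack: no quota or allowance is written, and a modest overshoot to 260 or 275 still leaves all five at 50 in only 1.7% or 21% of samples.

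A reader might infer three stronger things that the documents do not support:
- *The target is practically impossible.* The chance of five counts of exactly 50 is 250!/((50!)⁵ × 5²⁵⁰) = 0.00002, but this takes 250 literally, and any minimum set at one fifth of the total would fare much the same. The size of the likely shortfall is the fairer measure.
- *The oldest stratum must be the short one.* That follows for actual age if ages are uniform. For cognitive age it depends on a difference that the plan leaves open.
- *The threshold result will be biased.* Nothing here shows bias.

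The Methods Summary for Primary Aim #2 defines accurate use as agreement between the self-report and the child's reported change, and no analysis uses that definition. That gap would exist at any sample size, so it is a separate matter and adds no weight here.

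**Conclusion.** The statement of at least 50 per cognitive age is wrong as written: it leaves no slack, and the design cannot be expected to meet it in all five strata. That there is no slack needs no assumption. The size of the shortfall does. With random enrolment, equal shares and no loss, the smallest stratum is typically 42 rather than 50. With 10% or 20% missing BRIGANCE the average itself falls to 45 or 40. With uniform ages the actual-age year-7 band holds about 28, too few to have 10 children in each of three anchor categories.

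The effect is lost precision, mainly at the youngest or oldest year, in an analysis worded as exploratory. It should be corrected because the text promises a size that the plan does not secure, and because correction is cheap.

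**What to change.** - Replace the per-age minimum with the expected number in each year from about 250 after a stated allowance for missing BRIGANCE, and say whether 250 is enrolled or evaluable.
- Pre-specify that an end year is merged with its neighbour (3 with 4, or 7 with 6) when any of the three anchor categories in it has fewer than 10 children. This is the plan's own condition. A cut-off on the total, such as 30, would not secure it, as step 6 of the working shows. If the merged band still falls short, report it descriptively.
- Optional and separate, for Primary Aim #2: also model match between scale change and anchor on continuous cognitive age (logistic), using all children with a BRIGANCE. Report match within anchor category or corrected for chance, because the raw match rate depends on the mix of anchor answers.

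**Cost.** Rewording and a merge rule, plus one model if the option is taken; no extra patients. The stated per-age size becomes less favourable. The model has a real limit: with 200 to 225 children and accuracy rising only from 65% at age 4 to 70% at age 5 (assumed), the slope is non-significant in about 40% of simulated runs. The threshold age may then have no finite confidence interval and should be reported as not estimable.
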